9.2.1.3 Time to first GCA flare

The duration to first GCA flare from clinical remission up to 52 weeks for each group will be analyzed.

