11.4.2.3 Multiplicity considerations

In order to maintain an overall type I error of 0.01 a hierarchical testing approach will be used.

The testing sequence for the primary endpoint will be:

- Comparison of 200 mg versus placebo with 26 week taper for primary endpoint.
- Comparison of 200 mg versus placebo with 52 week taper for primary endpoint.
- Comparison of 150 mg versus placebo with 26 week taper for primary endpoint.
- Comparison of 150 mg versus placebo with 52 week taper for primary endpoint.

Since sarilumab 200 mg q2w is the primary dose for the study while sarilumab 150 mg q2w is added to provide additional information on efficacy and safety in GCA patients, the comparisons on the secondary endpoints will be focusing on the 200 mg q2w only.

After significance is established at a 0.01 level for all 4 comparisons on the primary endpoint as listed above, the following secondary endpoints will be tested sequentially as below:

- Total cumulative corticosteroid dose
- Time to first flare after remission

For each secondary endpoint, the comparison between 200 mg versus placebo + 26 week taper will be performed first; if significance is achieved at a 0.01 level, then the comparison between 200 mg versus placebo + 52 week taper will be performed.

Nominal p-values will be provided for the comparisons of all other secondary endpoints.

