1.6 STATISTICAL MODIFICATIONS MADE IN THE STATISTICAL ANALYSIS PLAN

Due to the early termination of the study and study discontinuation plan, a large amount of data will not be able to be collected since many enrolled patients will not complete all planned study visits and study procedures for the assessments of efficacy, ADA, and biomarker endpoints. In addition, the number of randomized patients is 83 in 4 arms (out of 360 planned) at the time of the premature termination of the study. The changes from the statistical analysis plan outlined in the protocol are summarized below.

- The primary endpoint for the study is sustained remission at Week 52. Based on patients' enrollment dates and the study discontinuation plan, only about 36 patients (out of 83) had an opportunity to complete the 52-week treatment period. For the cohort of patients who

did not have an opportunity to complete the 52-week treatment period, it is not meaningful to define the endpoint of sustained remission at Week 52. Therefore, the analysis of primary endpoint will be limited to the cohort of patients who had an opportunity to complete the 52-week treatment period. Details can be found in [Section 2.1.3.1](#) and [Section 2.4.4.1](#).

- Based on patients' enrollment dates and the study discontinuation plan, all patients should have had the opportunity to be treated for at least 24 weeks, so an additional endpoint, sustained remission at Week 24, is added in the SAP. Details can be found in [Section 2.1.3.1](#).
- Due to the same reason as mentioned above, the secondary endpoints of cumulative GTI scores at Week 52 will be limited to the cohort of patients who had an opportunity to complete the 52-week treatment period. In addition, the cumulative GTI scores will also be assessed at Week 24. Details are provided in [Section 2.1.3.2](#).
- The missing data imputation strategy for defining the endpoints of sustained remission at W24 and W52, and cumulative GTI scores at W24 and W52 can be found in [Section 2.1.3.1](#) and [Section 2.1.3.2](#), respectively; the rest of efficacy analyses will be based on data as observed, no missing data will be imputed.

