2.1.3.2 Secondary efficacy endpoint(s)

The following efficacy variables will be assessed:

- Components of sustained remission composite measure at Week 52 and Week 24
- Total cumulative corticosteroid (including prednisone) dose over during the treatment period
- Time to first GCA flare during the treatment period

- GTI Cumulative worsening score (CWS) and Aggregate improvement score (AIS) at Week 52 and Week 24.

Below are descriptions of these variables. Details related to imputation of GTI scores are described in [Section 2.5.2](#).

Components of sustained remission composite measure at Week 52

1. Proportion of patients who achieved disease remission by Week 12.
2. Proportion of patients who have no disease flare from Week 12 through Week 52.
3. Proportion of patients who have normalization of CRP (to <10 mg/L, with an absence of successive elevations to ≥ 10 mg/L) from Week 12 through Week 52.
4. Proportion of patients who successfully adhere to the prednisone taper from Week 12 through Week 52.

Components of sustained remission composite measure at Week 24

1. Proportion of patients who achieved disease remission by Week 12.
2. Proportion of patients who have no disease flare from Week 12 through Week 24.
3. Proportion of patients who have normalization of CRP (to <10 mg/L, with an absence of successive elevations to ≥ 10 mg/L) from Week 12 through Week 24.
4. Proportion of patients who successfully adhere to the prednisone taper from Week 12 through Week 24.

Total cumulative corticosteroid (including prednisone) dose during the treatment period

The total cumulative corticosteroid includes prednisone taper regimen per protocol, use of prednisone (an excess of ≤ 100 mg of prednisone during the study treatment period such as those employed to manage AE not related to GCA is permissible for meeting the definition of maintenance of sustained remission) and rescue corticosteroids dose prescribed for rescue therapy over the treatment period for GCA disease only.

Time to first GCA flare during the treatment period

The duration (in days) from randomization to first GCA flare after clinical remission and up to 52 weeks. Patients who never achieve remission will be censored at randomization day; and those who achieved clinical remission and never flared will be censored at the end of treatment assessment date up to Week 52.

The definition of GCA flare is provide in [Section 2.1.3.1](#) primary efficacy endpoint.

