2.3.1 Efficacy populations

Week 52 Analysis set: The primary endpoint for the study is sustained remission at Week 52. Based on patients' enrollment dates and the study discontinuation plan, not all the patients had an opportunity to complete the 52-week treatment period. For the cohort of patients who did not have an opportunity to complete the 52-week treatment period, it is not meaningful to define the endpoint of sustained remission at Week 52. Therefore, the analysis of primary endpoint will be limited to the Week 52 Analysis set, which includes the cohort of patients who had an opportunity to complete the 52-week treatment period. This cohort of patients is defined as the patients with a randomization date prior to *Oct 16, 2019* (i.e., *Oct 13, 2019*+3 days IMP administration time window, where *Oct 13, 2019* is 1-year before the targeted last patient last EOT visit date [i.e., *Oct 13, 2020*] according to the study discontinuation plan), which contains a total of 36 patients (out of 83 randomized patients).

For the same reason, the analysis of secondary endpoint of cumulative GTI scores at Week 52 will also be limited to the cohort of patients who had an opportunity to complete the 52-week treatment period.

For the rest of the efficacy endpoints, the primary analysis population will be the ITT population as defined in [Section 2.3.1.1](#).

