2.3.1.1 Intent-to-treat population

The intent-to-treat (ITT) population is the randomized population analyzed according to the treatment group allocated by randomization.

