2.4.4.2 Analyses of secondary efficacy endpoints

Components of sustained remission composite measure at Week 52 and Week 24

Descriptive statistics (i.e., counts and percentages) will be provided for the following binary variables by treatment groups:

- Patients who achieve disease remission by Week 12
- Patients who have absence of disease flare from Week 12 through Week 52 (or Week 24)
- Patients who have normalization of CRP (decrease to <10 mg/L) with sustained normalization from Week 12 through Week 52 (or Week 24)
- Patients who successfully adhere to the prednisone taper from Week 12 through Week 52 (or Week 24)

Total cumulative corticosteroid (including prednisone) dose

Descriptive statistics including the number of subjects, mean, and median of the total cumulative prednisone (or equivalent) dose will be presented for each treatment group. The difference between the medians and the corresponding 95% non-parametric confidence interval along with

p-value from the non-parametric Wilcoxon rank-sum test between the two combined treatment groups will also be provided.

The total cumulative CS dose will be based on the total number of days with complete or partial intake, no imputation will be done on missed tablets. Patients who received increased prednisone or equivalent in rescue therapy will be included in their original treatment groups.

In the scenario that a patient has already taken external CS for the disease before randomization on the day of randomization, the CS dose taken will be considered as the first dose of oral IMP. The first dose of prednisone per tapering regimen will be skipped, and the patient will take the second dose of prednisone on the next day.

Time to first GCA flare during the treatment period

Time (from randomization) to the first GCA flare after clinical remission up to Week 52 will be analyzed by Kaplan-Meier method providing the median, 25th and 75th percentiles (where possible) along with the 95% CI for the median. The comparison between the two combined groups will be performed using Cox proportional hazards model with prednisone dose at baseline (<30 mg/day or ≥30 mg/day) included as a covariate. Hazard ratio and the corresponding 95% CI and p-value will be provided.

Composite GTI and Specific List

GTI analyses

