Appendix C Summary of statistical analyses

Endpoint	Analysis		Statistical	Supportive	Subgroup	Other
	Population	Primary Analysis	Method	Analysis*	Analysis*	Analyses*
Primary Endpoint						
Patients who achieved sustained remission at Week 52	ITT	Proportion of patients achieving sustained remission at Week 52	CMH test stratified by baseline prednisone dose for combined groups, and descriptive analysis for non-combined groups.	1) Sensitivity analysis;2) Analysis excluding patients who prematurely withdraw from the study due to early termination of the study	No	No
Additional endpoint: Patients who achieved sustained remission at Week 24	ITT	Proportion of patients achieving sustained remission at Week 24	CMH test stratified by baseline prednisone dose for combined groups, and descriptive analysis for non-combined groups	Sensitivity analysis	No	No
Secondary Endpoints						
Patients who achieved of disease remission by Week 12	ITT	Proportion of patients who achieved of disease remission by Week 12	Descriptive	No	No	No
Patients who have absence of disease flare from Week 12 through Week 24 and Week 52	ITT	Proportion of patients who have absence of disease flare from Week 12 through Week 24 and Week 52	Descriptive	No	No	No
Patients who have normalization of CRP (decrease to <10 mg/L) with sustained normalization from Week	ITT	Proportion of patients who have normalization of CRP (decrease to <10 mg/L) with sustained normalization from Week 12 through Week 24 and Week 52	Descriptive	No	No	No

Endpoint	Analysis		Statistical	Supportive	Subgroup	Other
	Population	Primary Analysis	Method	Analysis*	Analysis*	Analyses*
12 through Week 24 and Week 52						
Patients who successfully adhere to the prednisone taper from Week 12 through Week 24 and Week 52	ITT	Proportion of patients who successfully adhere to the prednisone taper from Week 12 through Week 24 and Week 52	Descriptive	No	No	No
Total cumulative prednisone (or equivalent) dose	ITT	Total cumulative prednisone (or equivalent) dose over 52-week treatment period	Descriptive	No	No	No
Time to the first GCA flare after clinical remission up to Week 52	ITT	Time (from randomization) to the first GCA flare after clinical remission up to Week 52	Kaplan-Meier estimates and Cox proportional hazards model for combined groups, and descriptive analysis for non-combined groups.	No	No	No

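### Time to first flare is filed under ITT but compares only patients who reached remission, and its clock moves from remission to randomization without being listed as a change

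*SAP*

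**What the plan says.** Protocol 9.2.1.3 starts the clock at remission: "The duration to first GCA flare from clinical remission up to 52 weeks for each group will be analyzed". Protocol 11.4.2.3 names the same endpoint "Time to first flare after remission". Protocol 11.4.2.2 describes censoring only for study withdrawal and has no rule for patients who never remit. Protocol 11.3.1.1 puts all efficacy analyses on ITT.

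SAP 2.1.3.2 and 2.4.4.2 start the clock at randomization but still count only flares after clinical remission. Appendix C words it as "Time (from randomization) to the first GCA flare after clinical remission up to Week 52" and gives ITT as the population. For never-remitters, SAP 2.1.3.2 says: "Patients who never achieve remission will be censored at randomization day". SAP 2.4.4.2 compares the combined sarilumab groups with the combined placebo groups by Cox model: "Hazard ratio and the corresponding 95% CI and p-value will be provided".

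On the population, SAP 2.3.1 says "For the rest of the efficacy endpoints, the primary analysis population will be the ITT population", and 2.3.1.1 says "The intent-to-treat (ITT) population is the randomized population analyzed according to the treatment group allocated by randomization".

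SAP 1.6 introduces its list with "The changes from the statistical analysis plan outlined in the protocol are summarized below". The list covers the Week 52 cohort, the Week 24 endpoint, the GTI scores, imputation, significance level and combined groups, multiplicity and subgroups. It mentions neither the flare clock nor the never-remitter rule.

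**The concern.** There are two separate issues.

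**Population.** Remission occurs after randomization and can depend on treatment. An analysis confined to remitters therefore does not carry the protection of randomization, whatever its label. No listed output gives the number left out. The Week 12 remission table is not that number: it counts rescue for active GCA or treatment withdrawal before Week 12 as failure, whereas the clinical remission used for this endpoint has neither that rule nor a Week 12 limit. In addition, the flare definition in SAP 2.1.3.1 does not require prior CRP normalization. A patient whose symptoms resolve while CRP stays at 10 mg/L or above, and who then has a symptomatic recurrence with rescue, has a flare under 2.1.3.1 but is a never-remitter here, so the flare is not counted.

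**Clock.** With the origin at randomization and only post-remission flares counted, the time before remission is event-free by construction. If one group remits earlier, it can appear to flare earlier. A timing difference is plausible because remission requires CRP below 10 mg/L, and SAP 2.4.4.1 acknowledges that sarilumab acts directly on acute phase reactants.

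This is one of the few endpoints with a between-group estimate, interval and p-value, so readers will use it.

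**Working it through.** **The plan's own figure.** The documents give no HR, event count, power or remission timing for this endpoint. The nearest figure is SAP Table 1, used here only for group sizes. A two-sided pooled chi-square power for 53% of 42 v 17% of 41 gives 82.34% at alpha 0.01 and 94.47% at 0.05, against 82.3% and 94.5% stated.

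**Step 1: who enters the comparison.** The Cox partial likelihood is the product over events i of exp(b·x_i) / Σ exp(b·x_j), with the sum over patients j whose time T_j ≥ t_i. A never-remitter has T_j = 0, which is below every t_i > 0, so the patient appears in no denominator and has no event. The same holds for Kaplan-Meier. In simulation, censoring at zero and deleting these patients gave the same HR in every scenario.

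**Step 2: how many.** The documents give no never-remission rates. Protocol 6.5 expects most patients to be in remission by Week 12 in usual care, so low rates are more plausible. At an assumed 10% v 5%: 41 × 0.10 ≈ 4 placebo and 42 × 0.05 ≈ 2 sarilumab patients drop out of the comparison.

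**Step 3: selection, equal remission timing, no flare effect.** Assumptions: 200,000 patients per arm; severity s ~ N(0,1); flare hazard 0.015/week × exp(s) from remission; never-remission correlated with s from -0.35 to 0.95. HR is sarilumab v placebo.
- Never-remission 5% placebo v 2% sarilumab: 0.99-1.06
- 10% v 5%: 0.98-1.08
- 30% v 10% (outer bound): 0.92-1.34

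Values below 1 come from a negative link with severity, values above 1 from a positive link, and about 1.00 from none. The SAP clock and the remission clock agree within 0.001, so this part does not come from the SAP's change of origin.

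**Step 4: clock.** Write T = R + U, with R the time to remission and U the time from remission to flare. The SAP analyses T; the protocol analyses U. Assume no flare effect, and R uniform on 2-6 weeks (sarilumab) v 2-12 weeks (placebo). Follow-up is 52 weeks, or shortened to match early termination (36 of 83 to Week 52, the rest 24-52 weeks). The third model keeps the randomization clock but lets each patient enter the risk set at R.

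| Assumed flare hazard | SAP clock | Remission clock | Randomization clock, delayed entry |
|---|---|---|---|
| Constant | 1.08-1.10 | 0.99-1.00 | 0.95-1.00 |
| Rising to Week 26, or peaking at Week 24, from randomization | about 1.01-1.05 | 0.88-0.96 | 0.98-1.00 |

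Single runs on the SAP clock reached 1.00 and 1.11. The second row matters because protocol section 4 reports relapse in over 50% when steroids are tapered, and protocol Appendix B indexes the taper to weeks from randomization. With a milder gap (2-9 v 2-12 weeks), the SAP clock gives 1.05 under constant hazard and 1.00-1.02 under taper-linked hazard; under taper-linked hazard the remission clock gives 0.95-0.99. Under constant hazard and the wider gap, the Kaplan-Meier 25th percentile is 24.0 weeks (placebo) v 20.8 (sarilumab) on the SAP clock, and 16.9 v 16.7 on the remission clock.

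**Step 5: scale.** At 41 v 42 patients the SD of log HR is 0.33-0.42. For 1.10: log = 0.095, and 0.095/0.42 to 0.095/0.33 is 0.23-0.29 SD. For 0.88: |log| = 0.128, or 0.30-0.39 SD.

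**Step 6: why not count non-remission as an event.** With equal flare hazard after remission and remission of 70% v 50%, scoring never-remitters as events at Week 12 gives HR 0.76; with 80% v 40% it gives 0.57. A CRP effect on remission would then be read as a flare effect.

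**The case against.** The strongest reply is that little here is new or hidden. Conditioning on remission is in the protocol's own name for the endpoint, and a clock starting at remission already left never-remitters without an origin while the protocol also named ITT. The SAP rule fills that gap rather than contradicting text. The words about clinical remission appear wherever the SAP defines the endpoint, efficacy is descriptive and p-values are nominal. Patients are on prednisone 20-60 mg/day at randomization, and eligibility asks for symptoms and raised ESR or CRP only within the 6 weeks before baseline. Some may therefore meet remission at or soon after baseline, which would shrink any timing gap. All of that stands and limits the consequence.

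A reader might infer three stronger things that the documents do not support:
- **That the SAP broke an intact ITT analysis.** The restriction to remitters was inherited.
- **That rescue in never-remitters disappears.** It counts against Week 12 remission or taper adherence, adds to cumulative steroid dose and appears in disposition. One limb of the flare definition is also a recurrence, which presupposes earlier resolution. What is missing is any time-to-event analysis covering all randomized patients.
- **That the protocol's clock is right and the SAP's wrong.** If flare risk follows the taper, the SAP clock is close to neutral and the remission clock can show a benefit of sarilumab that does not exist.

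These replies leave two things unanswered: the population label is inaccurate, and the change of origin is not listed in SAP 1.6.

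**Conclusion.** The point holds on the text. The analysis filed under ITT is a comparison of patients who reached clinical remission, and the clock differs from the protocol's without being listed as a change. Severity is minor to moderate.

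The size is uncertain, and confidence in it is low because every remission rate, remission time and hazard shape is assumed. Under a 2-6 v 2-12 week gap with no flare effect, the SAP clock gives about 1.01-1.10 and the remission clock about 0.88-1.00, both well under half an SD of the log HR at this sample size. Selection bias has no fixed direction and is near zero if remission rates and timing are equal or if never-remission is unrelated to flare risk. Because all p-values are nominal, the issue affects how the HR and the Kaplan-Meier curves are read, not a confirmatory test.

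**What to change.** 1. Label the estimate, including the population column of Appendix C, as *ITT patients who reached clinical remission*, and report the number of never-remitters per group.
2. Add a supportive analysis in all randomized patients: time from randomization to first rescue therapy for active GCA, or for elevated ESR attributable to active GCA, whether or not remission was reached. Censor event-free patients at the end of treatment assessment, up to Week 52. Tabulate the two rescue reasons separately, because ESR is also an acute phase reactant. State that it answers a different question and is not immune to timing: in the 2-6 v 2-12 week scenario it gives 1.07-1.10 if flare risk starts only at remission, and 1.00 if risk runs from randomization.
3. Do not simply swap the origin. Report the protocol's remission-origin HR beside the randomization-clock HR, and add a randomization-clock Cox model with delayed entry at remission, which removes the event-free interval (0.95-1.00 across the assumed hazards).
4. Do not count failure to reach CRP-based remission as an event.
5. List the change of origin and the never-remitter rule in SAP 1.6.

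**Cost:** SAP wording, one line of counts, one derived variable, one extra table and two further Cox fits, all from eCRF fields already collected. The downside is a headline estimate no longer described as ITT, and several HRs to explain instead of one.

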10.4.4 Handling of patients after permanent treatment discontinuation

Every effort should be made to maintain patients in the study after permanent study treatment discontinuation. Patients should be followed up according to the study procedures as specified in this protocol up to the scheduled date of study completion, or up to recovery or stabilization of any AE to be followed up as specified in this protocol, whichever comes last. The scientific value of the complete collection of data will be explained to patients, and site personnel will receive training regarding strategies for patient retention, and access to tools to assist with this during the study.

If a patient prematurely and permanently discontinues study treatment, a premature EOT visit (see [Section 10.4.2](#)) should be scheduled at the time of treatment discontinuation, if possible. If not possible, the EOT should be scheduled as soon as possible after treatment discontinuation. The IRT should be notified of EOT. Of note, during this premature EOT visit, the bone density test does not need to be performed if it has been less than 6 months since the bone density test from the baseline visit.

Following the premature EOT visit, the remaining visits will be performed as scheduled. All efforts should be made to follow the patients for safety at least 6 weeks after the last dose of SC IMP and for primary endpoint, key secondary endpoints a through the remainder of the study visits up to Week 52 after premature EOT.

All cases of permanent treatment discontinuation should be recorded by the Investigator in the appropriate pages of the CRF when considered as confirmed. Details recording the specific reasons for discontinuation should be collected.

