11.4.2.2 Analyses of secondary efficacy endpoints

Other binary endpoints will be analyzed as described for the primary endpoint.

The cumulative prednisone dose will be analyzed using a nonparametric van Elteren test stratified by baseline prednisone dose and the mean and median dose will be summarized.

Time events will be analyzed by Kaplan-Meier method. Treatment groups will be compared with the use of Cox proportional hazards models, with adjustment for the baseline prednisone dose. Data censoring will be used for patients who withdraw from the study.

The GTI assessment (total score and domain-specific scores) will be analyzed with a mixed model repeated measures (MMRM) approach. The model, including treatment, visit, treatment-by-visit interaction, baseline prednisone dose (< 30 mg/day or ≥ 30 mg/day) as fixed effects and baseline score as a covariate, will be used to test the difference of least-square means (LS means) between treatment groups. Descriptive statistics including number of subjects, mean, standard error and LS means will be provided. In addition, difference in LS means, the corresponding 99% CI and the p-value will be provided.

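### Time to first flare is censored at the end-of-treatment visit although the protocol follows early stoppers to Week 52, so the hazard ratio is not the ITT estimate that SAP Appendix C describes

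*SAP*

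**What the plan says.** The SAP titles the endpoint "Time to first GCA flare during the treatment period" (2.1.3.2) and defines it as "The duration (in days) from randomization to first GCA flare after clinical remission and up to 52 weeks". Patients who never remit are handled separately. For the rest, "those who achieved clinical remission and never flared will be censored at the end of treatment assessment date up to Week 52". SAP 2.4.4.2 compares combined sarilumab with combined placebo by a Cox model and reports a hazard ratio, 95% CI and p-value. Appendix C gives the population as ITT and the analysis as "Time (from randomization) to the first GCA flare after clinical remission up to Week 52".

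Protocol 9.2.1.3 reads "The duration to first GCA flare from clinical remission up to 52 weeks for each group will be analyzed" and carries no on-treatment limit. On censoring, Protocol 11.4.2.2 says "Data censoring will be used for patients who withdraw from the study". Protocol 10.4.4 places a premature EOT visit at the time of discontinuation. It then says "Following the premature EOT visit, the remaining visits will be performed as scheduled", and asks that the primary and key secondary endpoints be followed "through the remainder of the study visits up to Week 52 after premature EOT". Protocol 10.4.5 separates stopping treatment from withdrawing from follow-up. Protocol 11.4.2.3 makes time to first flare one of the two secondary endpoints in the tested sequence.

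SAP 1.6 lists the changes from the protocol's analysis plan. The censoring of time to flare is not among them.

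**The concern.** For a patient who completes treatment, the EOT visit is the Week 52 visit and the two documents agree. For a patient who stops early and keeps attending, they part. The protocol keeps that patient under observation for flare, while the SAP ends the time at risk on the day of the premature EOT visit.

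This matters if flare risk changes at that moment, and there is reason to think it may. Under Protocol 10.4, permanent sarilumab discontinuation also takes the patient off the prednisone taper, so both study drugs change together. Censoring at that point would then be informative. Early stopping may also be more common on sarilumab. Protocol 10.4.3 requires permanent stopping for marked neutropenia, thrombocytopenia or ALT elevation, and Protocol 4.1 lists neutropenia as an identified risk and the other two as potential risks.

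This is the only efficacy endpoint for which a hazard ratio is planned. In a trial reported descriptively, that estimate and its interval are what readers will use, so its estimand needs to be clear.

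**Working it through.** **1. No figure to reproduce.** The documents give no event count, hazard ratio or power for time to flare, and no early-stopping rate. The check is therefore a comparison of the rules, followed by an illustration on stated assumptions.

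**2. The rules side by side.** Take a remitter who stops SC drug at Week 16 for a reason of their own and stays in follow-up.

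| Course after the stop | Protocol follow-up | SAP, natural reading | SAP, literal reading |
|---|---|---|---|
| Flares at Week 22 | Event at Week 22 | Censored at Week 16 | Event at Week 22 |
| No flare to Week 52 | Censored at Week 52 | Censored at Week 16 | Censored at Week 16 |

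The natural reading follows the endpoint's title. The literal reading follows the censoring clause, which covers only those who never flared, together with the 52-week limit. Under the literal reading, a patient stays in the risk set after Week 16 only if a flare is going to occur, and the 52 − 16 = 36 flare-free weeks of the second patient are discarded. That overstates the hazard in whichever arm has more early stoppers. Neither reading is the ITT analysis to Week 52.

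**3. How many flares could be affected (assumed).** Count = N × share stopping early × share of those flaring afterwards by Week 52, with 10–30% stopping and 20–50% flaring:
- All randomized: 83 × 0.10 × 0.20 = 1.7, up to 83 × 0.30 × 0.50 = 12.4.
- Week 52 Analysis set: 36 × 0.10 × 0.20 = 0.7, up to 36 × 0.30 × 0.50 = 5.4.

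The first range is a ceiling. It treats all 83 as remitters with follow-up to Week 52, and only about 36 could have completed 52 weeks.

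**4. Effect on the hazard ratio, natural reading (assumed).** The simulation uses 40,000 patients per arm and exponential times. Half of placebo patients flare by Week 52, which is a hazard of ln 2 / 52 = 0.0133 per week. The on-drug hazard ratio is 0.40. Stopping times are exponential with rate −ln(1 − d)/52, where d is the arm's early-stop share. After stopping, the sarilumab hazard is either unchanged (×1) or back at the placebo level (0.40 × 2.5 = 1.0). The placebo hazard never changes. All patients are followed to Week 52.

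| Stop share, sarilumab / placebo | Sarilumab hazard after stop | HR, follow-up to Week 52 | HR, EOT censoring | Flares lost |
|---|---|---|---|---|
| 10% / 10% | unchanged | 0.396 | 0.394 | 4.6% |
| 20% / 10% | unchanged | 0.403 | 0.403 | 6.3% |
| 30% / 10% | unchanged | 0.392 | 0.391 | 8.3% |
| 30% / 30% | unchanged | 0.399 | 0.397 | 14.5% |
| 10% / 10% | placebo level | 0.422 | 0.399 | 6.2% |
| 20% / 10% | placebo level | 0.452 | 0.403 | 9.6% |
| 30% / 10% | placebo level | 0.491 | 0.411 | 13.1% |
| 30% / 30% | placebo level | 0.477 | 0.397 | 19.4% |

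With an unchanged hazard, the two rules agree within each setting, and the spread from 0.391 to 0.403 is simulation noise. With a return to placebo risk, EOT censoring gives a lower ratio, from 1 − 0.399/0.422 = 5% lower to 1 − 0.397/0.477 = 17% lower.

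**The case against.** The strongest reply is that the SAP sentence does not say later flares are dropped. It censors only those who never flared, the window runs to 52 weeks, and Appendix C repeats Week 52. A reader might infer from the endpoint's title that post-EOT flares are certainly excluded; the text does not settle that. This objection stands against stating the loss as fact. It does not rescue the rule, because the literal reading mixes post-EOT events with risk time that stops at EOT.

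A reader might also infer that the protocol censors at study withdrawal and nowhere else. Protocol 11.4.2.2 names withdrawal but does not say it is the sole reason, and censoring at Week 52 is implicit. It remains true that stopping treatment is not named.

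The scope is narrow. Under the discontinuation plan in SAP 1.1, patients stopped by the sponsor have one further visit 6 weeks after treatment ends, so EOT censoring is essentially administrative for them. The point concerns patients who had remitted, stopped for other reasons and stayed in follow-up. Their number is not given.

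The flare definition is awkward after an early stop. SAP 2.1.3.1 ties a corticosteroid increase to the taper or to its completion, and a patient who has left the taper fits neither limb cleanly. This stands, and the fix must deal with it.

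Finally, efficacy is descriptive, p-values are nominal, and a while-on-treatment estimand is legitimate in a terminated trial. It then has to be declared as one. Here the change is not listed and Appendix C still labels the analysis ITT to Week 52.

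**Conclusion.** The point holds as a conflict between the SAP's censoring rule and the protocol's endpoint and follow-up, not disclosed in SAP 1.6. Under either reading of SAP 2.1.3.2 the hazard ratio is not the protocol's ITT estimate, and it may be biased if flare risk changes after stopping.

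Under the natural reading the likely direction favours sarilumab. That rests on two assumptions the documents do not quantify: that sarilumab patients' flare risk rises after stopping, and that enough of them stop early while staying in follow-up. If the hazard does not change, the effect is nil. In the illustration, a return to placebo risk makes the reported ratio about 5% to 17% lower than under full follow-up. These are not estimates for this trial.

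Two stronger readings are not supported. A reader might treat the share of flares lost as the change in the hazard ratio, but earlier censoring also removes time at risk, so the ratio moves less. A reader might also take all the laboratory stopping criteria as established sarilumab effects. Protocol 4.1 puts only neutropenia in that class, and Protocol 10.4.1 provides for temporary interruption first at moderate values. The change should be made, but it concerns an estimate and its interpretation, not a confirmatory test.

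**What to change.** In SAP 2.1.3.2:
- Count the first flare after remission up to Week 52 whether or not SC or oral study drug has stopped. Identify it by the existing entry on the steroid medication page (rescue therapy for active GCA, or for elevated ESR attributable to it), and state that this applies after the patient has left the taper.
- Censor non-flarers at the earliest of Week 52, last GCA assessment and study withdrawal.
- For patients stopped by the sponsor's termination, state in advance whether censoring is at EOT or at the last GCA assessment.
- Keep EOT censoring as a supportive analysis labelled while-on-treatment, with later flares excluded.

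Align the title in 2.1.3.2 and 2.4.4.2 with Appendix C, and list the handling in SAP 1.6.

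The cost is a few sentences, a changed censoring date and one additional model run. No new data collection is needed, since GCA assessments and steroid use are already scheduled for recording. The drawback is that some added flares will have occurred off study drug; the supportive analysis shows the result without them. P-values stay nominal.
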